7.1.9 PROCEDURES FOR DOCUMENTING PREGNANCY DURING STUDY

Subjects who are pregnant or expect to become pregnant during the course of the study up to Week 36 will be excluded from participation in the study. Should a subject become pregnant after receiving the first study treatment in the study, she will not be given any further study treatments. A Pregnancy Form will be completed by the site personnel and submitted to the sponsor or its designee within 24 hours after learning of the pregnancy. Site personnel will submit the Pregnancy Form to the Sponsor or its designee by fax, as described in Section 7.4.2.

The investigator will also report this event to the IRB within 24 hours of becoming aware of the pregnancy. Sites must request the subject's permission to query pregnancy outcome and follow each subject to determine the outcome of the pregnancy. Results will be summarized in the clinical study report (CSR).

Subjects who become pregnant at any point during the study will continue to be followed for safety assessments without receiving further study treatment. Procedures that are contraindicated during pregnancy, including additional treatments, must not be performed. Investigators should use clinical judgment regarding subsequent study-related blood collection based on the presence or absence of anemia in each subject.

All pregnancies that occur from the time of first study treatment through the follow up visits must be reported. The investigator will monitor the subject and follow the outcome of the pregnancy. If the end of the pregnancy occurs after the study has been completed, the outcome will be reported directly to the study team and the medical monitor.

7.2 METHODS AND TIMING OF THE COLLECTION AND RECORDING OF SAFETY DATA

Non-serious AEs and SAEs (and UADEs) will be collected for each subject from the time when informed consent is obtained through Week 88.

The sources of AEs cover:

- 1. The subject's response to questions about her health (a standard non-leading question such as 'How have you been feeling since your last visit?' is asked at each visit).
- 2. Symptoms spontaneously reported by the subject.
- 3. Evaluations and examinations where the findings are assessed by the investigator to be clinically significant changes or abnormalities.
- 4. Other information relating to the subject's health becoming known to the investigator (e.g. hospitalization).

All AEs will be reported on the appropriate CRF. Any SAE (or UADE) occurring during the course of the study must be reported to the sponsor within 24 hours of awareness.

7.3 SAFETY AND TOXICITY MANAGEMENT

The Medical Monitor will be responsible for the overall safety monitoring of the study.

Safety assessments include the following:

- Incidence of all adverse events classified by system organ class (SOC), preferred term, severity, and relationship to study treatment
- Local and systemic injection site review; special attention will be paid to the examination of the injection site. Administration site reactions and the subject's complaints will be documented.

7.3.1 ADVERSE EVENTS OF SPECIAL INTEREST

Adverse events of special interest (AESI) are the adverse events deemed related to VGX-3100/placebo delivered with CELLECTRA[™] 5PSP that require expedited communication from the Site to the Sponsor and meet any of the following criteria:

- Grade 3 or greater persistent administration site erythema, and/or induration recorded ≥ 2 hours immediately after Study Treatment
- Grade 4 or greater persistent administration site pain, tenderness recorded ≥ 2 hours immediately after Study Treatment
- Grade 3 or greater fever
- Grade 3 or greater systemic symptoms, including generalized pruritus

Sites will inform the Sponsor via method described in section 7.4.1 within 24 hours to discuss whether further dosing for the particular subject should continue.

7.3.2 STOPPING RULES (CRITERIA FOR PAUSING OF STUDY)

- If at any time during a study one-third (1/3) or more of the subjects experience an AESI, verified per protocol definition, further enrollment and study treatment will be halted until a thorough review has been conducted by the Medical Monitor, Principal Investigator for the trial, and the DSMB. Only the DSMB may review unblinded data in making their recommendation to the Sponsor regarding continuation of a trial.
- If any SAE (or potentially life-threatening AE), or death verified as related to study treatment occurs, further enrollment and study treatment will be halted until a thorough review has been conducted by the Medical Monitor, Principal Investigator for the trial, IRB (if applicable) and the DSMB.
- If three or more subjects in this study, experience the same Grade 3 or 4 unexpected adverse event, verified per protocol definition and assessed as related to study treatment, further enrollment and study treatment will be halted until a thorough review has been conducted by the Medical Monitor, Principal Investigator for the trial, and the DSMB.
- In the event of two identical, unexpected, Grade 4 toxicities, verified per protocol definition and assessed as related to study treatment, further enrollment and study treatment will be

halted until a thorough review has been conducted by the Medical Monitor, Principal Investigator for the trial, IRB (if applicable) and the DSMB.

The sponsor or designee will notify all investigators and IRBs/EC (if required) regarding the outcome of any investigation stemming from a Study Pause.

Guidelines for assessing clinical abnormalities are in Section 7.1 in general and in the Table provided in Section 7.1.5.

Guidelines for assessing relatedness are detailed in Section 7.1.6.

7.4 STUDY REPORTING PERIOD OF ADVERSE EVENTS

All solicited and unsolicited adverse events will be collected throughout the study and recorded on the AE CRF.

7.4.1 STUDY REPORTING PERIOD OF ADVERSE EVENTS OF SPECIAL INTEREST

Adverse events of special interest (AESI) (see Section 7.3.1) require expedited communication from the Site to the Sponsor. Within 24 hours of the site's awareness of the event, AESI must be reported by the Investigator through data entry in the Adverse Event electronic case report form (eCRF) via the Medidata RAVE electronic data capture (EDC) system. In the event that the Medidata RAVE EDC system is unavailable, the investigator must notify the Sponsor via email or phone.

AESI reporting if EDC system is unavailable

EMAIL:	
SAFETY PHONE:	

7.4.2 STUDY REPORTING PERIOD OF SERIOUS ADVERSE EVENTS

The reporting period for SAEs (without regard to causality or relationship) is comprised of the period following the signing of the informed consent form until the end of the study. Each AE will be assessed to determine whether it meets seriousness criteria. If the AE is considered serious, the investigator should record this event to the Sponsor within 24 hours of becoming aware of the event. The investigator may also directly report this event to the Ethics Committee according to its standard operating procedures. Expectedness of SAEs will be determined by the Sponsor using reference safety information specified in the Investigator's Brochure.

An event may qualify for expedited reporting to regulatory authorities if it is an SAE, unexpected per reference safety information and considered related following the guidelines in Section 7.1.3 (Suspected Unexpected Serious Adverse Reaction, SUSAR) and 7.1.4 (Unanticipated [serious] adverse device effect) in line with relevant legislation. All investigators will receive a safety letter notifying them of relevant SUSAR reports. The investigator should notify the Institutional Review Board (IRB)/ Institutional Ethics Committee (IEC) as soon as is practical, of serious events in writing where this is required by local regulatory authorities, and in accordance with the local institutional policy.

At any time after completion of the SAE reporting period, if an investigator becomes aware of an SAE that is suspected by the investigator to be related to the study drug, the event will be reported to the Sponsor or its designee. If the investigator becomes aware of an SAE in a study subject after the last scheduled follow-up visit, and considers the event related to prior Study Treatment, the investigator will report it to the Sponsor or the appropriate designee.

Within 24 hours of the site's awareness of the event, all SAEs (regardless of relationship to investigational product) must be reported by the Investigator through data entry in the Adverse Event electronic case report form (eCRF) via the Medidata RAVE electronic data capture (EDC) system. In the event that the Medidata RAVE EDC system is unavailable, the paper SAE Report form should be used and faxed to the PPD Pharmacovigilance (PVG) Safety Hotline Fax Number shown below:

Facsimile (FAX) reporting if requireda:

Americas FAX#:	
Europe FAX#:	

a: Reporting by FAX is required for paper SAE Report Forms if electronic data capture (EDC) is not available, redacted supporting medical records, and Pregnancy Report Forms.

All supporting documents for SAE reports, including medical records and diagnostic test results, will include reference to the study subject number. The study site will redact all other subject identifying information present on SAE supporting documents prior to sending the report to the Sponsor. The supporting documents for SAE reports should be sent by fax to the PPD PVG Safety Hotline Fax Number, shown above.

Investigator will supply the Sponsor and the IRB with more information as it becomes available and any additional requested information. The Sponsor or its representative will be responsible for determining and in turn, reporting SAEs to regulatory authorities according to the applicable regulatory requirements. SAEs must be followed by the investigator until resolution, even if this extends beyond the study-reporting period. Resolution of an SAE is defined as the return to baseline status or stabilization of the condition with the expectation that it will remain chronic.

In the event of death, if an autopsy is performed, a copy of the report will be sent to the Sponsor.

7.4.3 NOTIFICATION OF SERIOUS ADVERSE EVENTS

In accordance with local regulations, the Sponsor shall notify the appropriate regulatory authorities, and all participating investigators in a written safety report of any adverse experience associated with the use of the product that is both serious and unexpected and any significant new safety information that might materially influence the benefit-risk assessment of a medicinal product, sufficient to consider changes in product administration or overall conduct of a clinical investigation. The Sponsor will notify regulatory agencies within the time frame specified by local requirements but no later than 10 working days for UADE, 7 days for a fatal or life-threatening SUSAR and 15 days for all other SUSARS (see Section 7.1.3 and 7.1.4).

7.4.4 REPORTING OF DEVICE RELATED COMPLAINTS

A product complaint (or device deficiency) involves any written, electronic, or oral communication that alleges deficiencies related to the identity, quality, durability, reliability, safety, effectiveness, or performance of a device such as malfunction, misuse or use error and inadequate labeling. A malfunction is defined as the failure of a device to meet its performance specifications or otherwise perform as intended. The intended performance of a device refers to the intended use for which the device is labeled. All product complaints that meet this definition must be reported to the sponsor with 10 days of discovery. Any product complaint that involves an AE or SAE must be also reported per Section 7.4.

Any problems experienced including potential malfunctions of the device, error messages displayed on the device screen following treatment or errors that occur during the treatment procedure must be reported to the Sponsor or designee immediately for evaluation.

Additional instructions on reporting to be provided separately.

7.5 STUDY DISCONTINUATION

Inovio Pharmaceuticals reserves the right to discontinue the study at this site or at multiple sites for safety or administrative reasons at any time. In particular, a site that does not recruit at a reasonable rate may be discontinued. Should the study be terminated and/or the site closed for whatever reason, all non-source documentation and study product pertaining to the study must be returned to Inovio Pharmaceuticals or its representative.

The study may be discontinued at any time by an IRB, Inovio Pharmaceuticals Inc., the FDA or other government agencies as part of their duties to ensure that research subjects are protected.

8 STATISTICAL ANALYSIS PLAN

8.1 GENERAL CONSIDERATIONS

The statistical analysis of the data will be performed by Inovio Pharmaceuticals or its representative.

This is a two-arm, multi-center, placebo-controlled, blinded, and randomized clinical trial in subjects with a histologic diagnosis of cervical HSIL. The study's primary endpoint is binary: regression to CIN1/normal and clearance of HPV-16 and/or HPV-18 infection, based on tissue collected at Week 36. The primary hypothesis is that VGX-3100 will be superior to placebo regarding the proportion who achieve the primary endpoint. Secondary efficacy analyses involve regression to CIN1/normal, clearance of HPV-16 and/or HPV-18 infection from cervical tissue and non-progression of cervical lesions. Other secondary analyses concern safety and humoral and cellular immunological measures. Exploratory analyses concern tissue immunological measures, durability of clearance of HPV-16 and/or HPV-18 infection from cervical tissue, association of colposcopy, cytology, virology, other microRNA (miRNA) profiles, and DNA methylation profile and efficacy, patient-reported outcomes, and association of Immunoscore and efficacy.

8.2 RANDOMIZATION AND BLINDING

Subjects will be randomized (2 VGX-3100:1 Placebo) in a stratified manner according to a) the degree of CIN observed in the biopsy specimens at screening (CIN2 vs. CIN3), b) BMI category

(≤25 vs. >25 kg/m²) on Day 0, and c) age category (<25 years vs. ≥25 years) on Day 0. There will be no pre-determined number of subjects required to be randomized within each stratum. To ensure that milder CIN2 disease is not over-represented in the study, the percentage of subjects enrolled with CIN2 will not exceed 50% of the total enrolled. A group of sequential allocation numbers will be designated for use by each participating country.

The study is double-blinded.

8.3 SAMPLE SIZE/POWER

A sample of 198 subjects will be randomized to receive either 6 mg VGX-3100 or placebo IM followed by EP in a 2:1 ratio. This sample size provides 90% power to declare VGX-3100 superior to placebo, assuming the true proportion of subjects who achieve the primary endpoints is 35% and 14% for VGX-3100 and placebo, respectively. These proportions also incorporate missing data (~10%) classified as non-regressors (failures). The assumptions are based on the Phase 2 study results.

8.4 ANALYSES POPULATIONS

Analysis populations will include:

- The intention to treat (ITT) population includes all subjects who are randomized. Subjects in this sample will be grouped to treatment arms as randomized. Analysis of the ITT population will be primary for the analysis of efficacy in this study.
- The modified intention to treat (mITT) population includes all subjects who receive at least one dose of Study Treatment and who have the analysis endpoint of interest. Subjects in this sample will be grouped to treatment arms as randomized. Analysis of the mITT population will be considered supportive for the corresponding ITT population for the analysis of efficacy.
- The per-protocol (PP) population comprises subjects who receive all doses of Study Treatments and have no protocol violations and who have the analysis endpoint of interest. Subjects in this sample will be grouped to treatment arms as randomized. Analyses on the PP population will be considered supportive of the corresponding ITT population for the analysis of efficacy. Subjects excluded from the PP population will be identified and documented prior to unblinding of the study database.
- The safety analysis set includes all subjects who receive at least one does of Study Treatment. Subjects will be analyzed as to the treatment they received.

8.5 **SUBJECT DISPOSITION**

Disposition will be summarized by treatment arm for the ITT population and will include the number and percentage randomized, the number and percentage who received each dose and the number who completed the trial. The number and percentage of subjects who discontinued will be summarized overall and by reason. The number in each analysis population will also be presented.

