8.17 INTERIM ANALYSIS

For reasons of futility (early evidence of poor efficacy of VGX-3100) or safety issues, the DSMB could recommend stopping enrollment at any time; no formal interim analysis will be performed for this purpose. The type I error of 0.05 will not be adjusted for possible early stopping due to futility.

Group-level unblinded (VGX-3100, Placebo) summaries and analyses of efficacy will be produced once the primary endpoint Week 36 visit data are completed for all subjects; subject-level blinding will be maintained. Long-term follow-up data will continue to be collected for all subjects with remaining visits through the final Week 88 visit. The summaries and analyses will allow the Sponsor to have results with respect to the primary endpoint and all other efficacy endpoints corresponding to the cervix and the Week 36 visit on which to make decisions regarding the VGX-3100 program, while still gathering secondary and exploratory endpoint and safety data through the final Week 88 visit. The planned set of summaries and analyses is comprised of a) the primary composite endpoint of histopathologic regression and virologic clearance, b) the secondary

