endpoint of histopathologic regression, c) the secondary endpoint of virologic clearance, d) the secondary composite endpoint of histopathologic regression to normal and virologic clearance, e) the secondary endpoint of histopathologic regression to normal, and f) the secondary endpoint of histopathologic non-progression. None of these summaries or analyses will be provided if the total count of subjects who experience the event of interest is greater than 0 and the count for any treatment group relative to this total count is less than 3% for a given summary/analysis. Also, items a) through f) are planned to be produced in the order in which they are listed, but as there are intersecting endpoints among these items, items among b) through f) will not be produced if the difference in total count of subjects who experience the event of interest is greater than 0 and the count for any treatment group is 0, relative to any preceding item in the set. The group-level unblinded (VGX-3100, Placebo) production of the summaries and analyses will not include anyone directly involved with the trial or any additional unblinded personnel; only the external Contract Research Organization (CRO), PPD, which has already been providing unblinded summaries for the Data Safety Monitoring Board, will be utilized. Thus, the trial will remain blinded with respect to subject treatment assignment throughout the trial. The type I error of 0.05 will not be adjusted for this procedure.

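### The deadline for fixing per-protocol exclusions was not moved when version 5.0 added a Week 36 release of arm-level efficacy results to the Sponsor

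*Protocol*

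**What the plan says.** Section 8.4 (version 5.0) defines the PP population as subjects who received all doses, who "have no protocol violations and who have the analysis endpoint of interest". Its role is secondary: "Analyses on the PP population will be considered supportive of the corresponding ITT population for the analysis of efficacy". The main analysis set is stated separately: "Analysis of the ITT population will be primary for the analysis of efficacy in this study". The deadline for the PP list is: "Subjects excluded from the PP population will be identified and documented prior to unblinding of the study database".

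Section 8.17, which section 2.5 and the synopsis largely repeat, describes the group-level unblinding. The arm-level efficacy outputs "will be produced once the primary endpoint Week 36 visit data are completed for all subjects; subject-level blinding will be maintained". Their purpose is that they "will allow the Sponsor to have results with respect to the primary endpoint and all other efficacy endpoints corresponding to the cervix" at Week 36, so that decisions about the programme can be taken while data collection continues to Week 88. Only the external contract research organisation produces the output, small counts are suppressed, and individual assignments stay blinded to the end of the trial. The section closes on error control: "The type I error of 0.05 will not be adjusted for this procedure".

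**The concern.** A PP deadline exists so that nobody decides who is excluded while knowing how the comparison came out. The 8.4 sentence did that job when it was written. In the two earlier protocol versions in the same file, 8.17 planned no formal interim analysis, and only the DSMB was to see unblinded data. Version 5.0 placed a Sponsor-facing readout before the end of the study but left the deadline attached to the unblinding of the database.

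At stake is the credibility of a supportive analysis. If the PP result is offered as agreeing with the ITT result, a reader will ask whether the exclusions were settled before or after the ITT comparison was known. As written, the protocol cannot answer that.

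**Working it through.** The point is one of timing, so the check sets the passages in order.

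1. **Deadline.** The 8.4 sentence is identical in the earliest version in the file, in version 4.0 and in version 5.0.

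2. **New event.** Version 5.0 adds the group-level release, triggered when Week 36 data are complete for all subjects. The recipient is the Sponsor. Under 8.1 the analysis is performed by the Sponsor or its representative.

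3. **Which event is the unblinding of the database?** Sections 2.5 and 8.17 keep the trial blinded to individual assignment throughout. The natural reading is therefore the end of the study, after Week 88, and the order becomes: Week 36 data complete, arm-level results to the Sponsor, follow-up to Week 88, PP deadline.

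4. **Length of the open interval.** For the last subject, 88 - 36 = 52 weeks lie between the two visits. The interval from release to unblinding is shorter by the time needed to complete the Week 36 data and longer by the time needed to close the database after Week 88.

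5. **Can the list still change in that interval?** The 8.4 definition puts no time limit on violations. Section 4.3.4 gives failure to return for visits as an example of a protocol violation, and visits continue at Weeks 62 and 88. Read literally, an event after the release could remove a subject from a Week 36 analysis.

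6. **What cannot change.** ITT comprises all randomized subjects, so PP decisions cannot alter it. The plan's own sample size also stands: 132 versus 66 subjects, 35% versus 14%, one-sided 0.025, gives power 0.903, matching the stated 90% with 198 subjects.

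7. **How far blinding limits the risk.** With 2:1 allocation and the planned rates, a responder is on VGX-3100 with probability 2 × 0.35 / (2 × 0.35 + 0.14) = 0.70 / 0.84 = 83%. For a non-responder it is 2 × 0.65 / (2 × 0.65 + 0.86) = 1.30 / 2.16 = 60%. Even someone who knew a subject's outcome would hold only partial information about her arm. As an assumed borderline case, take 34/132 versus 9/66: 25.8% - 13.6% = 12.1 points, one-sided score-test p = 0.026. Removing 20 non-responders without knowledge of arm, in proportion to the 98 and 57 non-responders (about 12.65 and 7.35), gives 34/119.35 - 9/58.65 = 28.5% - 15.3% = 13.1 points and p = 0.028. Such removal shifts the estimate but does not create significance.

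**The case against.** The best defence is that producing group-level results requires joining treatment codes to the data, so the 8.4 wording could already mean before that first unblinding. That reading is possible. It sits awkwardly with the statement that the trial stays blinded at subject level throughout, and a deadline with two readings about a year apart needs the same edit. The safeguards in 8.17 and the supportive role of the PP set also count, and they hold the point to a modest one.

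A reader might infer more, and the documents do not support it:

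- **That the type I error needs adjusting, or that the confirmatory test is undefined.** The release follows complete Week 36 data for all subjects, 8.9 states one test at one-sided 0.025, and later follow-up adds no primary endpoint data. Making no adjustment is correct.
- **That Week 36 data can be edited after release.** The protocol names no data lock, but nothing in it permits later edits. A lock may be set in the statistical analysis plan, which was not at hand, or in data management documents.
- **That the Sponsor knows each subject's outcome.** No passage says so. Section 6.2.11 shows only that adjudicated Week 36 histology is reviewed at the Week 40 call.
- **That the bias can be sized by deleting non-responders and watching the difference rise above 21 points.** Deletion without regard to arm needs no release, so it measures nothing the release causes. The 21 points is also the ITT difference. The planned rates count about 10% missing as failures (8.3), and the PP set excludes subjects without the endpoint. Dropping those alone gives 35/0.9 - 14/0.9 = 38.9% - 15.6% = 23.3 points.

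**Conclusion.** The point holds as a timing gap in 8.4. Followed literally, the protocol lets PP exclusions for a supportive Week 36 analysis be settled after the Sponsor has seen the arm-level results, with 52 weeks between the last subject's Week 36 and Week 88 visits. The primary ITT analysis and the type I error statement are sound. No bias in the PP estimate can be quantified from the document, and the maintained subject-level blind limits it.

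The conclusion rests on two assumptions: that database unblinding means the end of the study, and that those who settle the PP list are not shielded from the released results. The protocol does not settle either explicitly.

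**What to change.** In 8.4, for the PP population used for Week 36 efficacy endpoints, replace the deadline with: *prior to the production of the Week 36 group-level unblinded summaries*. Add that any later change to that list is logged with its reason and reported only as a sensitivity analysis.

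The cost is one clause and one added sentence, plus completing the review of protocol violations through Week 36 before the release instead of after Week 88. Sample size, primary analysis and error control stay as they are.
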